9.3.4. Study Discontinuation

Both the sponsor and the investigator reserve the right to terminate the study at any time. Should this be necessary, both parties will arrange discontinuation procedures and notify the appropriate regulatory authority(ies) and IECs. In terminating the study, Gilead and the investigator will assure that adequate consideration is given to the protection of the subjects' interests.

11. APPENDICES

- Appendix 1. Investigator Signature Page
- Appendix 2. Pregnancy Precautions, Definition for Female of Childbearing Potential, and Contraceptive Requirements

Idelalisib has insufficient data to exclude the possibility of a clinically relevant interaction with hormonal contraception that results in reduced contraception efficacy. Therefore, contraceptive steroids are not recommended as a contraceptive method either solely or as a part of a contraceptive regimen. Data from clinical pharmacokinetic interaction studies of idelalisib have demonstrated no adverse effect on fertility or embryo-fetal development. However, there is no clinical data of idelalisib in pregnant women. Please refer to the latest version of the investigator's brochure for additional information.

b) Contraception Requirements for Female Subjects of Childbearing Potential

The inclusion of female subjects of childbearing potential requires using a highly effective contraceptive measure. They must also not rely on hormone-containing contraceptives as a form of birth control during the study. They must have a negative serum pregnancy test at Screening and a negative pregnancy test on the Baseline/Day 1 visit prior to randomization. At minimum, a pregnancy test will be performed at the end of relevant systemic exposure. In the event of a delayed menstrual period (over one month between menstruations), a pregnancy test must be performed to rule out pregnancy. This is even true for women of childbearing potential with infrequent or irregular periods. They must also agree to one of the following from Screening until 30 days after the end of relevant systemic exposure.

Complete abstinence from intercourse of reproductive potential. Abstinence is an acceptable method of contraception only when it is in line with the subject's preferred and usual lifestyle.

Or

Consistent and correct use of 1 of the following methods of birth control listed below.

- Intrauterine device (IUD) with a failure rate of <1% per year
- Tubal sterilization
- Ensure micro-insert system (provided confirmation of success 3 months after procedure)
- Vasectomy in the male partner (provided that the partner is the sole sexual partner and had confirmation of surgical success 3 months after procedure)
- Barrier methods (one female barrier and one male barrier must be used in combination)
 - Female barriers: Diaphragm with spermicide or Cervical cap with spermicide
 - Male barriers: Male condom (with or without spermicide)

Female subjects must also refrain from egg donation and in vitro fertilization during treatment and until at least 30 days after the end of relevant systemic exposure

3) Contraception Requirements for Male Subjects

Male subjects must also refrain from sperm donation during treatment and until at least 90 days after the end of relevant systemic exposure.

It is theoretically possible that a relevant systemic concentration may be achieved in a female partner from exposure of the male subject's seminal fluid. Therefore, male subjects with female partners of childbearing potential must use condoms during treatment until the end of relevant systemic exposure.

4) Unacceptable Birth Control Methods

Birth control methods that are unacceptable include periodic abstinence (eg, calendar, ovulation, symptothermal, post-ovulation methods), withdrawal (coitus interruptus), spermicides only, and lactational amenorrhea method (LAM). Female condom and male condom should not be used together.

5) Procedures to be Followed in the Event of Pregnancy

Subjects will be instructed to notify the investigator if they become pregnant at any time during the study, or if they become pregnant within 30 days of last idelalisib dose. Subjects who become pregnant or who suspect that they are pregnant during the study must report the information to the investigator and discontinue idelalisib immediately. Subjects whose partner has become pregnant or suspects she is pregnant during the study must report the information to the investigator. Instructions for reporting pregnancy, partner pregnancy, and pregnancy outcome are outlined in Section [7.6.2.1](#).

## LIST OF ABBREVIATIONS

AE	adverse event
ALT	alanine aminotransferase
AST	aspartate aminotransferase
BMI	body mass index
CSR	clinical study report
CTCAE	Common Terminology Criteria for Adverse Events
DMC	data monitoring committee
eCRF	electronic case report form
HLGT	high-level group term
HLT	high-level term
LLT	lower-level term
LOQ	limit of quantitation
MedDRA	Medical Dictionary for Regulatory Activities
PT	preferred term
SAE	serious adverse event
SAP	statistical analysis plan
SOC	system organ class
StD	standard deviation
TEAE	treatment-emergent adverse event
TFLs	tables, figures, and listings
ULN	upper limit of normal

## **1. INTRODUCTION**

This statistical analysis plan (SAP) describes the statistical analysis methods and data presentations to be used in tables, figures, and listings (TFLs) in the clinical study report (CSR) for Study GS-US-313-2120. This SAP is based on Protocol GS-US-313-2120 Amendment 3 dated 4 November 2016 and the electronic case report form (eCRF). The SAP will be finalized before database finalization. Any changes made after finalization of the SAP will be documented in the CSR.

### **1.1. Study Objectives**

The primary objective of this study is as follows:

- To provide idelalisib, a marketed PI3K $\delta$  inhibitor, in lieu of GS-9820, an investigational second generation PI3K $\delta$  inhibitor, to subjects receiving GS-9820 in Study GS-US-315-0102 at the time of study closure who have had objective evidence of clinical benefit defined as at least stable disease on imaging assessed by the IRC and no toxicities prior to enrollment in this study that would preclude initiating therapy with idelalisib. Idelalisib and GS-9820 are both in the class of agents that inhibit PI3K $\delta$  and as such this exchange of class for class agent is warranted and acceptable.

### **1.2. Study Design**

This study is an open-label, rollover study to provide idelalisib to subjects receiving GS-9820 in Study GS-US-315-0102 at the time of study closure.

### **1.3. Sample Size and Power**

There is no formal hypothesis to be tested in this study; therefore, no formal sample size calculation was performed.

A total of 3 subjects were enrolled in Study GS-US-313-2120.

## **2. TYPE OF PLANNED ANALYSIS**

### **2.1. Interim Analyses**

This study does not have a data monitoring committee (DMC). Therefore, no analyses will be conducted for the DMC.

### **2.2. Final Analysis**

After all subjects have completed the study, outstanding data queries have been resolved or adjudicated as unresolvable, and the data have been cleaned and finalized, the final analysis of the data will be performed.

### **3. GENERAL CONSIDERATIONS FOR DATA ANALYSES**

By-subject listings will be presented for all subjects in the Safety Analysis Set and sorted by subject identification (ID) number, visit date, and time (if applicable). Data collected on log forms, such as AEs, will be presented in chronological order within the subject. Age, sex at birth, race, and ethnicity will be included in the listings, as space permits.

#### **3.1. Analysis Sets**

Analysis sets define the subjects to be included in an analysis. Analysis sets and their definitions are provided in this section. The analysis set will be identified and included as a subtitle of each listing.

##### **3.1.1. Safety Analysis Set**

The Safety Analysis Set includes all subjects who took at least 1 dose of study drug. This is the primary analysis set for safety analyses.

#### **3.2. Subject Grouping**

Not Applicable.

#### **3.3. Strata and Covariates**

This study does not use a stratified randomization schedule when enrolling subjects. No covariates will be included in safety analyses.

#### **3.4. Examination of Subject Subgroups**

There are no prespecified subject subgroupings for safety analyses.

#### **3.5. Multiple Comparisons**

Adjustments for multiplicity will not be made, because no formal statistical testing will be performed in this study.

#### **3.6. Missing Data and Outliers**

##### **3.6.1. Missing Data**

In general, missing data will not be imputed unless methods for handling missing data are specified.

##### **3.6.2. Outliers**

All data will be included in the data analysis.

### **3.7. Data Handling Conventions and Transformations**

In general, age (in years) on the date of the first dose of study drug will be used for analyses and presentation in listings. For screen failures, the date the informed consent was signed will be used for age calculation. If only the birth year is collected on the CRF, “01 July” will be used for the unknown birth day and month for the purpose of age calculation. If only birth year and month are collected, “01” will be used for the unknown birth day.

### **3.8. Analysis Visit Windows**

#### **3.8.1. Definition of Study Day**

Study day will be calculated from the first dosing date of study drug and derived as follows:

- For postdose study days: Assessment Date – First Dosing Date + 1
- For days prior to the first dose: Assessment Date – First Dosing Date

Therefore, study day 1 is the day of first dose of study drug administration.

#### **3.8.2. Analysis Visit Windows**

The nominal visit as recorded on the eCRF will be used.

## **4. SUBJECT DISPOSITION**

### **4.1. Subject Enrollment and Disposition**

The following by-subject listing will be provided by subject ID number in ascending order:

- Reasons for premature study drug discontinuation

### **4.2. Extent of Study Drug Exposure**

A by-subject listing of study drug administration will be provided by subject ID number (in ascending order) and visit (in chronological order).

### **4.3. Protocol Deviations**

Protocol deviations occurring after subjects entered the study are documented during routine monitoring. A by-subject listing will be provided for those subjects with important protocol deviations.

## **5. BASELINE CHARACTERISTICS**

### **5.1. Demographics**

A by-subject demographic listing, including age, sex, race, and ethnicity, will be provided by subject ID number in ascending order.

### **5.2. Medical History**

Medical history will be collected at screening for general conditions (ie, conditions not specific to the disease being studied).

General medical history data will not be coded, but will be listed only.

## **6. EFFICACY ANALYSES**

No efficacy analyses will be conducted for this study.

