- 5) Evidence of a personally signed informed consent indicating that the subject is aware of the neoplastic nature of their disease and has been informed of the procedures to be followed, the experimental nature of the therapy, alternatives, potential benefits, possible side effects, potential risks and discomforts, and other pertinent aspects of study participation.

Exclusion Criteria

Subjects who meet any of the following exclusion criteria are not eligible to be enrolled in this study:

- 1) Known hypersensitivity or intolerance to any of the active substances or excipients in the formulation of idelalisib.

- 2) Toxicities that would preclude initiating therapy with idelalisib prior to enrollment (eg, history of drug-induced pneumonitis, ongoing inflammatory bowel disease)
- 3) Concurrent participation in another therapeutic clinical trial.
- 4) Pregnant or breastfeeding
- 5) Ongoing infection, treatment, or prophylaxis for CMV within the past 28 days.

Study Procedures/
Frequency: All subjects will receive idelalisib 150 mg taken orally, twice per day (BID) continuously. Subjects will undergo disease assessments and receive medical care per institutional standards of care.

Test Product, Dose, and Mode of Administration: Idelalisib: 150 mg taken orally BID starting on Day 1 and administered continuously thereafter.

Reference Therapy, Dose, and Mode of Administration: None

Criteria for Evaluation:

Safety: Overall safety profile characterized by the type, frequency, severity, timing of onset, duration, and relationship to study therapy of \geq Grade 3 adverse events (AEs), serious adverse events (SAEs), and deaths.

Efficacy: Investigator response assessments

Statistical Methods: Safety will be assessed by incidence of \geq Grade 3 AEs, SAEs, and deaths. Efficacy will be evaluated by investigator response assessments. Both safety and efficacy will be assessed using data collected from subjects who received at least 1 dose of idelalisib. All analyses will be limited to descriptive summaries and listings.

Sample Size: Up to 6 subjects

This study will be conducted in accordance with the guidelines of Good Clinical Practice (GCP) including archiving of essential documents.

GLOSSARY OF ABBREVIATIONS AND DEFINITION OF TERMS

AE	adverse event
ALT	alanine aminotransferase
ANC	absolute neutrophil count
AST	aspartate aminotransferase
AUC	area under the concentration versus time curve
β-HCG	beta human chorionic gonadotropin
BID	bis in die (twice daily)

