8.3. Analysis Sets

Both safety and efficacy will be assessed using data collected from subjects who received at least 1 dose of idelalisib.

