8.4. Analysis Methods

All the analyses will be limited to descriptive summaries and listings. Categorical variables will be summarized with the number and percentage of subjects in each category. Continuous variables will be summarized by presenting n, mean, standard deviation, median, Q1, Q3, minimum and maximum.

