9.1.5. Study Files and Retention of Records

The investigator must maintain adequate and accurate records to enable the conduct of the study to be fully documented and the study data to be subsequently verified. These documents should be classified into at least the following two categories: (1) investigator's study file, and (2) subject clinical source documents.

The investigator's study file will contain the protocol/amendments, CRF and query forms, IEC and governmental approval with correspondence, informed consent, drug records, staff curriculum vitae and authorization forms, and other appropriate documents and correspondence.

The required source data should include sequential notes containing at least the following information for each subject:

- Subject identification (name, date of birth, gender);
- Birth dates will be collected as per local regulatory requirements, as needed
- Documentation that subject meets eligibility criteria, ie, history, physical examination, and confirmation of diagnosis (to support inclusion and exclusion criteria);
- Documentation of the reason(s) a consented subject is not enrolled
- Participation in study (including study number);

- Study discussed and date of informed consent;
- Dates of all visits;
- Documentation that protocol specific procedures were performed;
- Results of efficacy parameters, as required by the protocol;
- Start and end date (including dose regimen) of idelalisib, including dates of dispensing and return;
- Record of all adverse events and other safety parameters (start and end date, and including causality and severity);
- Concomitant medication (including start and end date, dose if relevant; dose changes);
- Date of study completion and reason for early discontinuation, if it occurs.

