#### **7.5. Changes From Protocol-Specified Safety Analyses**

There are no deviations from the protocol-specified safety analyses.

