## 10. APPENDIX 1 SCHEDULE OF ASSESSMENTS

Period	Screen	Treatment															
		1	2	3	4	5	6	7	8	9	10	11	12	13	14	15+	End of study
Visit	1	2	3	4	5	6	7	8	9	10	11	12	13	14	15+		
Week	-4	0	2	4	6	8	10	12	14	16	18	20	22	24	Q4 weeks	Q12 weeks	
Study Day	Within -28 days	1	14	28	42	52	70	84	98	112	126	140	154	168			
Visit Window			±2	±2	±2	±2	±2	±2	±2	±2	±2	±2	±2	±2	±7	±7	
Informed consent	X																
Serum β-HCG a	X																
Pneumococcal, Hib, Tetanus titers	X																
ALT/AST/total bilirubin	X	X		X		X		X		X				X		X	X
Urine pregnancy test a		X		X		X		X		X				X		X	X
ANC b	X	X	X	X	X	X	X	X	X	X	X	X	X	X			
CMV surveillance	X			X		X		X		X		X		X	X c		
Immune Monitoring	X			X				X						X		X	X
Assess adverse events and SAEs d		X		X		X		X		X				X		X	X
Record concomitant medications e		X		X		X		X		X				X		X	X
Idelalisib dispensing/accounting		X		X		X		X		X				X		X	X
Investigator response assessment f	X			X		X		X		X				X		X	X

- Abbreviations: β-HCG=beta human chorionic gonadotropin, ALT=alanine aminotransferase, AST=aspartate aminotransferase, Hib = Haemophilus Influenzae Type B
- a For women of child bearing potential; Serum β-HCG to be collected at screening, urine pregnancy test to be collected at visits from first dose of idelalisib to EOS
- b Absolute neutrophil count (ANC) will be monitored at least every two weeks for the first 24 weeks of idelalisib treatment
- c CMV surveillance must be conducted approximately every 4 weeks throughout the course of idelalisib treatment
- d For an AE of Diarrhea/Colitis: 1) Obtain history of onset and duration of diarrhea, including description of number of stools and stool composition, travel history, dietary changes and a medication review to identify possible diarrheogenic agents and 2) Perform physical examination including assessment for fever, dizziness, abdominal pain/cramping, and weakness
- e Concomitant medications only collected if it is related to an AE
- f Record investigator response assessment if obtained per standard of care

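### The protocol promises an efficacy evaluation from investigator response, but the SAP plans no efficacy output and does not declare the change

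*SAP*

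**What the plan says.** **Protocol.** The synopsis names investigator response as the efficacy criterion and, under Statistical Methods, states: "Efficacy will be evaluated by investigator response assessments". Section 8.3 fixes the population: "Both safety and efficacy will be assessed using data collected from subjects who received at least 1 dose of idelalisib". Section 8.4 fixes the form: "All the analyses will be limited to descriptive summaries and listings". Table 6-1 schedules the response assessment at screening and on treatment, and Section 6.3 includes it among the end-of-study procedures. Section 9.1.5 lists, among the required source data, "Results of efficacy parameters, as required by the protocol".

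**SAP.** Section 6 consists of one sentence: "No efficacy analyses will be conducted for this study". Appendix 1 nevertheless keeps the response row, with footnote f: "Record investigator response assessment if obtained per standard of care". On changes from the protocol, Section 7.5 says: "There are no deviations from the protocol-specified safety analyses". Section 1 says: "Any changes made after finalization of the SAP will be documented in the CSR".

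**The concern.** The two documents disagree on whether efficacy is evaluated at all, and the SAP does not present its position as a departure or give a reason.

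Subjects enter because the independent review committee found at least stable disease at closure of the parent study (Protocol 4.2). Protocol 1.4 describes the hoped-for benefit of switching to idelalisib in terms of disease control. Investigator response is the only measure the protocol names for whether that control continued. If the SAP is followed as written, the CSR outputs will describe safety in these subjects and leave out the stated benefit measure, and a reader will not learn why.

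**Working it through.** The documents give no alpha, power or calculated sample size on this point, so there is no plan figure to reproduce. The check is a comparison of texts, followed by a count.

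**1. Protocol commitment against SAP provision**

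| Element | Protocol | SAP |
|---|---|---|
| Efficacy measure | Investigator response (synopsis) | None (6) |
| Population | At least one dose (8.3) | Safety Analysis Set, same definition, described for safety analyses (3.1.1) |
| Form | Descriptive summaries and listings (8.4) | No response output |
| Collection | Table 6-1, Section 6.3 | Row kept in Appendix 1 |

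**2. Could another SAP output carry response?** The listings that the SAP names are:
- reasons for premature drug discontinuation (4.1)
- drug administration (4.2)
- important protocol deviations (4.3)
- demographics (5.1)
- medical history (5.2)
- adverse events (7.1.6)
- laboratory data (7.2)
- subjects meeting liver criteria (7.2.2)
- prior and concomitant medications (7.3)
- pregnancy (7.4.1)

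None is a response listing. The general rule in SAP 3 sets the population and sort order of listings but does not name response.

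Progression could surface as a discontinuation reason, but that is not a dated response by visit. The safety listings cannot be relied on for it either. Under Protocol 7.5.1, progression unrelated to idelalisib is not treated as an SAE; it goes on the eCRF and is reported in the CSR where appropriate.

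**3. Is the change declared?** SAP 7.5 is confined to safety, so it is silent on efficacy rather than false. The commitment in SAP 1 covers changes made after finalization, whereas this one is in the SAP itself. The revision table in SAP 9 is empty. No stated route brings the change to the CSR reader.

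**4. Size.** Inputs: the response row of SAP Appendix 1, and 3 enrolled subjects (SAP 1.3).
- Marks per subject through Week 24: screening (1) plus Weeks 4, 8, 12, 16 and 24 (5) = 6.
- Maximum for 3 subjects: 6 × 3 = 18, made up of 1 × 3 = 3 pre-dose and 5 × 3 = 15 post-dose.
- End of study: 1 × 3 = 3 more, plus any 12-weekly entries after Week 24.
- Response listings specified in the SAP: 0.

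These counts are ceilings. They assume that all 3 subjects reach Week 24 and that every scheduled assessment is done and recorded.

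**The case against.** The strongest reply is that this is a drug-access study with 3 subjects, no primary endpoint (Protocol 3.1) and no hypothesis (SAP 1.3). Protocol Section 8 has a heading for safety endpoints and none for efficacy, and SAP 6 states the omission openly. On that view only a sentence of explanation is missing. All of this is true, and it limits the stakes. It does not remove the conflict: SAP 6 discloses the outcome without saying that it departs from the synopsis and Section 8.3. A small sample is a reason to avoid percentages, not to omit a listing, since the SAP lists every other data type for the same subjects.

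A second reply is that the by-visit record is weak evidence. Protocol 6.2.1 has the previous response recorded again when no change is identified and drug is dispensed, while footnote f has a response recorded only if standard care produced one. Entries may be carried forward or absent. This stands as a limit on interpretation, and the fix should make it visible.

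Third, the SAP does not prevent the CSR from describing response in the text. That is so, but nothing plans for it.

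Fourth, Section 9.1.5 concerns the investigator's source records and creates no duty to analyse. That is correct; it shows only that efficacy results are expected to exist.

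Finally, Section 8.4 calls for numbers and percentages for categorical variables, which a listing does not supply. For 3 subjects a listing is a reasonable reading of a section that provides for both summaries and listings.

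**Conclusion.** The concern holds. The protocol plans a descriptive efficacy evaluation from investigator response in dosed subjects; the SAP plans none, lists no response data and does not declare the change. Up to 18 scheduled entries through Week 24, of which 15 are post-dose, have no planned output, with end-of-study and 12-weekly entries in addition.

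No error rate, power or primary conclusion is affected. The point should be corrected because the conflict is direct and cheap to resolve.

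The conclusion assumes that the protocol text reviewed is the one the SAP was written against (Amendment 3, per SAP 1). The response row in the SAP's own schedule supports that assumption. The count further assumes that all 3 enrolled subjects were dosed.

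**What to change.** Replace the sentence in SAP 6 with wording such as:

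*Investigator response will be presented in a by-subject listing for the Safety Analysis Set, giving visit, assessment date where recorded, response, and date of progression where recorded. Entries that repeat an earlier response under Protocol 6.2.1 will be marked where the data allow. Because 3 subjects were enrolled, no percentages will be tabulated.*

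The marking matters because Protocol 6.2.1 and footnote f differ on whether an entry is made without a new assessment.

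If efficacy was dropped deliberately, say so and give the reason as a change from the protocol synopsis and Section 8.3, both in the SAP (a counterpart to 7.5) and in the CSR. That explains the gap but still leaves the response data without an output, so the listing is preferable.

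The cost is a short text change and one listing for 3 subjects, or a brief explanation. Response is already in the schedule, so no new data collection is needed. The eCRF is not among the documents, so which date fields exist cannot be confirmed; the wording above allows for that.
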